11.3.1 Immediate reporting

11.3.1.1 Reporting of SAEs to sponsor

SAEs observed throughout the study must be documented on an "SAE report" form in accordance with instructions for completing the "SAE report" form. This form and the instructions will be provided in the investigator file and must be completed and supplied immediately (within 24 h) to the sponsor (21CFR§ 312.32, 21CFR§ 312.64).

Any SAE that occurs throughout the study, whether or not related to the IMP or the medical device, must be reported by the investigator within 24 h by fax, or by e-mail, to the following contact data:

Email: [REDACTED]

Fax: [REDACTED]

The initial report must be as complete as possible, including details of the current illness and (serious) AE, and an assessment of the causal relationship between the event and the IMP or IMD or study procedures.

Information not available at the time of the initial report (e.g. an end date for the AE or laboratory values received after the report) must be documented on an “SAE report” form, with the box “Follow-up”/”Final report”.

The instructions for completing the “SAE report” form give more detailed guidance on the reporting of SAEs, and AEs initially reported as non-serious that become serious. In the latter situation, when a non-serious event becomes serious, details must be forwarded immediately (within 24 h) to the sponsor on an “SAE report” form.

Pregnancies occurring during a subject's participation in the study, although not typically considered SAEs, must be notified to the sponsor within the same timelines as an SAE (within 24 h after becoming aware of the pregnancy) on a pregnancy notification form. Further treatment will be addressed on a case-by-case basis with the treating physician and the investigator.

Any pregnancy should be followed up until completion. If relevant, the development of the newborn will be monitored for an appropriate time post-delivery.

The drug safety department of the sponsor or designee has to be notified by fax or e-mail.

The sponsor will ensure that all legal reporting requirements to the competent authorities and the IRB(s) are met.

Note:

For regulatory reporting purposes, events which are assessed by the sponsor as “unrelated” or “unlikely related” to the study medication will be considered as having no reasonable causal relation and will not be reported on an expedited basis.

Events assessed by the sponsor as “possibly, probably or definitely related” will be considered as having a plausible causal relation to the study medication and will be reported if they are also considered unexpected and serious.

11.3.1.2 Reporting of USADEs to the sponsor and to IRB

Events which can be clearly assigned to the IMD and which are assessed by the investigator as “possibly, probably or definitely related” to the IMD and which are both serious and unanticipated will be considered as unanticipated serious adverse device effect (USADE). A report of any USADE occurring during an investigation shall be submitted to the reviewing IRB and the sponsor within 10 working days after the investigator first learns of the effect (21 CFR §812.150).

In case a serious and unexpected event cannot be clearly assigned to the IMD, it should be treated as an SAE (see Section 11.1.2).

Note: Reporting of USADEs to the sponsor is equal to SAE reporting described in Section 11.3.1.1.

11.3.1.3 Reporting of expeditable adverse events to IRB

The investigator will promptly forward IND safety reports received from sponsor (see section 11.4.2) and report all unanticipated problems involving risk to human subjects or others, and changes in the research activity to the IRB.

11.3.2 Unblinding

This is an open-label study, i.e., unblinding is not applicable.

11.4 Documentation and reporting of adverse events by sponsor

11.4.1 Determination of expectedness, Reference Safety Information

Expectedness of serious AEs will be determined by the sponsor according to the designated Reference Safety Information (RSI). Any updates or substantial amendments will be considered accordingly. The RSI for the investigational products will be included in the IB 'ALA-AK-CT015-IB' in section 7.2.

Unexpected: An AE or suspected adverse reaction is considered unexpected if it is not listed in the RSI or is not listed with the specificity or severity that has been observed. Unexpected, as used in this definition, also refers to AEs or suspected adverse reactions that are mentioned in the RSI as occurring with a class of drugs or as anticipated from the pharmacological properties of the drug, but are not specifically mentioned as occurring with the particular drug under investigation.

11.4.2 Reporting of expeditable adverse events to competent authorities and investigators

The sponsor will report all serious and unexpected AEs, which are judged by the sponsor as having a reasonable suspected causal relationship (suspected unexpected serious adverse reaction - SUSAR) as IND safety reports to the FDA and all participating investigators according to applicable law.

The sponsor will also report USADEs to the FDA, all reviewing IRBs and to all investigators.

11.4.3 Periodic reporting of adverse events by sponsor

A summary of all Investigational New Drug (IND) safety reports will be included in the progress report submitted annually to the competent authorities within 60 days of the international anniversary date of the product (14 June, in agreement with authorities). The same report will also be submitted to the IRB(s) to ensure a continuing review of the project.

11.4.3.1 Development safety update report (DSUR)

The sponsor will prepare and submit annual safety reports to competent authorities and concerned ethics committees.

11.5 Continuous risk assessment

The sponsor's safety department will apply appropriate monitoring measures to continuously survey the benefit risk ratio of the IMP, the IMD and study procedures.

12 WITHDRAWALS

12.1 Withdrawal of subjects

Subjects must be **withdrawn from study** (i.e. from any further study procedure) for the following reasons:

- At their own request (withdrawal of informed consent).
- If, in the investigator's opinion, continuation in the study would be detrimental to the subject's well-being.

In all cases, the reason for and date of withdrawal must be documented. Subjects can withdraw consent at any time of the study without being obliged to specify a reason for their withdrawal. In case of an AE causing the withdrawal of consent, the AE has to be documented as cause of withdrawal.

As far as possible, all examinations scheduled for the final study day should be performed on all subjects who receive the IMP but who do not complete the study according to protocol.

For subjects that may not be treated due to screening failures or who decide to terminate the study prior to treatment, at least the following parameters must be documented in the eCRF: date of informed consent, demographics and date and reason for withdrawal.

12.2 Replacement of subjects

Subjects who discontinue will not be replaced.

12.3 Withdrawal of samples

In the data review meeting criteria for withdrawal of PK samples will be defined on case-by-case basis.

13.2 Emergency identification of investigational medicinal products

In this open-label study, all eligible subjects will receive one active treatment. For this reason, special emergency identification procedures are not applicable for this trial.

13.3 Emergency treatment

There is no substance-specific treatment for adverse reactions. For treatment of PDT associated pain and discomfort please see Section 9.2.

During and after a subject's participation in the trial, the investigator or institution should ensure that adequate medical care is provided to a subject for any AEs, including clinically significant laboratory values, related to the trial. The investigator or institution should inform a subject when medical care is needed for intercurrent illness(es) of which the investigator becomes aware.

14 STATISTICAL PROCEDURES

Subjects who withdraw from study participation before administration of PDT (including treatment field preparation) are considered screening failures. The demographic data, date of informed consent as well as date and reason for withdrawal from screening failures are entered into the clinical database and will not be passed through the data cleaning process. Their data are listed separately from data of treated subjects. A detailed overview of statistical procedures is provided in the SAP. The SAP will encompass demographics, PK and safety analysis.

14.1 Analysis variables

The primary endpoints for pharmacokinetics are the

- Baseline-adjusted plasma concentrations of ALA for obtaining baseline-adjusted plasma concentration-time curves
- Baseline-adjusted plasma concentrations of PpIX for obtaining baseline-adjusted plasma concentration-time curves

Secondary endpoints are the

- Baseline-adjusted AUC_{0-t} , baseline-adjusted $AUC_{0-\infty}$, baseline-adjusted C_{max} , T_{max} , $T_{1/2}$, and λ_Z for ALA (if data permit)
- Baseline-adjusted AUC_{0-t} , baseline-adjusted $AUC_{0-\infty}$, baseline-adjusted C_{max} , T_{max} , $T_{1/2}$, and λ_Z for PpIX (if data permit)
- Assessment of safety and tolerability of PDT with BF-200 ALA under maximal use conditions, including:
 - Frequency and severity of treatment-emergent adverse events (TEAEs), including serious adverse events (SAEs). TEAEs are defined as all AEs with onset or worsening after treatment with the investigational medicinal product and device.
 - Overall tolerability.
 - Application site skin reactions in the treatment field(s) during and post PDT.
 - Application site discomfort during and after illumination reported by the subjects.
 - Application site pain during PDT on an 11-point Numeric Rating Scale (NRS-11).
 - Vital signs data.
 - Safety laboratory data if clinically significant deviations occur.
 - Data from the physical examinations if clinically significant findings occur.

Tertiary endpoints are the

- Unadjusted plasma concentration-time curve for ALA and pharmacokinetic parameters of ALA: unadjusted AUC_{0-t} , unadjusted $AUC_{0-\infty}$, unadjusted C_{max} , T_{max} , $T_{1/2}$, and λ_Z if data permit

- Unadjusted plasma concentration-time curve for PpIX and pharmacokinetic parameters of PpIX: unadjusted AUC_{0-t} , unadjusted $AUC_{0-\infty}$, unadjusted C_{max} , T_{max} , $T_{1/2}$, and λ_z if data permit

All pharmacokinetic characteristics (AUC_{0-t} , $AUC_{0-\infty}$, $T_{1/2}$ and λ_z) will be derived from baseline-adjusted as well as unadjusted plasma concentrations of ALA and PpIX as described above.

The pharmacokinetic parameters for ALA and PpIX will be derived from plasma using noncompartmental methods and are listed in Table 6. Values < LLOQ and negative values after baseline adjustment are set to zero and disregarded when displaying data on a logarithmic scale.

Table 6: List of pharmacokinetic parameters

Parameter	Description
C_{max}	Observed maximum baseline-adjusted or unadjusted plasma concentration
AUC_{0-t}	Area under the baseline-adjusted as well as unadjusted plasma concentration-time curve from time zero to the last sampling time point at which the concentration was at or above lower limit of quantification (LLOQ); $t_{(last)}$ is defined as the last value > 0 after baseline adjustment. AUC_{0-t} will be calculated according to the linear trapezoidal formula
$AUC_{0-\infty}$	Area under the baseline-adjusted as well as unadjusted plasma concentration-time data extrapolated to infinity ($AUC_{0-\infty} = AUC_{0-t} + C_t/\lambda_z$)
$\%AUC_{t-\infty}$	Proportion of extrapolated part ($\%AUC_{t-\infty}$) ($1 - [AUC_{0-t}/AUC_{0-\infty}] \cdot 100$)
t_{max}	time to reach C_{max}
$t_{1/2,\lambda_z}$	apparent terminal half-life, calculated by $\ln 2/\lambda_z$
λ_z	Terminal rate constant λ_z denotes the terminal rate constant estimated by linear regression analysis from a range of concentrations in the terminal phase estimated for each treatment and subject by log-linear regression from the linear portion of the logarithmic transformed concentration-time plot. The algorithm will start with the last 3 points with quantifiable concentrations and increases the number of involved points by 1 until the time point after C_{max} restricted on time points after removing of the BF-200 ALA gel. For each regression an adjusted R^2 will be computed: $\text{Adjusted } R^2 = \frac{(1 - R^2) \cdot (n - 1)}{n - 2},$ where n denotes the number of data points ($n \geq 3$). The regression with the largest adjusted $R^2 > 0.8$ will be selected for the estimation of λ_z using WinNonlin option "BestFit".

14.2 Analysis sets

Any decision for exclusion of individual subjects from an analysis population will be made before database lock in a data review meeting; Documentation concerning which subjects are to be excluded from an analysis population will be prepared and reported, i.e., as data review minutes.

Enrolled set

All subjects enrolled in this study i.e. that provided informed consent to participate in the study.

Treated set

All subjects that received IMP treatment (including subjects whose PDT treatment was terminated for any reason without illumination). This set is the analysis set for the summary of subject discontinuation.

Safety set

The safety set (SAF) will include all subjects who undergo at least one of the following treatment procedures: preparation of the treatment field(s), application of BF-200 ALA, or illumination. The SAF is the analysis set for all safety analyses.

Pharmacokinetic sets

The pharmacokinetic sets are defined for each of the two analytes separately. The pharmacokinetic set per analyte includes all subjects who have at least one evaluable pre-dose and post dose pharmacokinetic sample (i.e., samples taken after the application of BF-200 ALA) for the respective analyte. A post dose sample is regarded evaluable if the plasma concentration is at or above LLOQ.

As plasma concentration data of ALA and PpIX are considered separately, e.g., a subject can be in the pharmacokinetic set for evaluation of PpIX but not for evaluation of ALA.

Subjects who develop bleeding during preparation of the treatment area are not to be excluded from the pharmacokinetic set.

14.3 Statistical methods

The planned analyses are of exploratory nature without any formal statistical hypotheses. All measured variables and derived parameters of subjects who are treated will be listed and, if appropriate, tabulated in summaries. For categorical variables, frequency counts and percentages will be used to summarize the results.

Descriptive statistics of continuous variables will be provided including number of observations, arithmetic mean, standard deviation (SD), coefficient of variation (CV) (if appropriate), median as well as minimum and maximum.

Descriptive statistics of pharmacokinetic parameters and plasma concentrations for ALA and PpIX additionally included the geometric mean, geometric SD, and geometric CV. If a zero occurs in a sample, the corresponding geometric mean and geometric SD will be computed, omitting this value.

The PK data will be presented for all subjects in the respective PK sets. Selected data may be presented excluding outliers as well. Safety data will refer to the SAF set.

Disposition of subjects and exposure

Descriptive analysis of subjects in each analysis set such as the enrolled set, the treated set, the SAF, the pharmacokinetic set for ALA and PpIX, respectively, will be presented. Premature discontinuation from the study and completion of the study will be summarized. Reasons for discontinuation will be tabulated.

PDT details (e.g. incubation time of the IMP, duration of illumination, interruptions/pauses, interferences) and sampling time points for PK blood samples will be presented overall and by strata.

Demographics and background characteristics

All variables concerning demographic and background characteristics will be summarized to describe the study population.

Concomitant medications will be coded according to Anatomical Therapeutic Chemical Classification System (ATC) and number and frequency of subjects with previous or concomitant medication will be summarized.

Safety analyses

All safety endpoints will be analyzed descriptively and in an exploratory way. These safety analyses will be performed for the safety set. Safety analyses will be conducted overall and according to strata.

AEs will be coded according to the latest Medical Dictionary for Regulatory Activities (MedDRA) version available at the day of database closure. The analysis will focus on the TEAEs. TEAEs will be summarized and tabulated according to primary system organ class and preferred term. TEAEs leading to death and TEAEs resulting in discontinuation of study will be tabulated using frequency tables if a reasonable number of AEs of this type are observed.

A listing of subjects with AEs will be provided for all AEs reported and all subjects enrolled.

The frequency of application site skin reactions and of application site discomfort will be presented overall and per strata. The mean and the maximal pain score (NRS-11) and the respective confidence intervals (CIs) will be presented overall and per strata.

All laboratory values will be classified as normal or abnormal according to the laboratory's normal ranges and indicated as clinically significant or non-clinically significant by the investigator. Out of range laboratory values that are considered clinically significant will be documented in the medical history (Visit 1) or as AEs (Visit 3) and listed as such.

The analyses of variables for vital signs will focus on the evaluation of the change from baseline to the scheduled time point after baseline. Descriptive analysis (number of subjects, mean, median and SD, minimum, maximum) of the time course and of changes from baseline to post baseline time point will be presented.

General physical examinations will include the following body systems: head and neck, skin, lymph nodes, thorax including heart and lung, abdomen, and musculoskeletal, peripheral vascular and nervous system. All clinically significant abnormal physical findings will be listed. Details of further analyses will be specified in the statistical analysis plan (SAP).

Pharmacokinetics

Descriptive statistics of unadjusted and baseline-adjusted plasma concentrations for ALA and PpIX by nominal blood sampling time will be provided.

The following graphics will be provided for ALA and PpIX:

- Geometric mean concentrations (unadjusted and baseline-adjusted) will be given on linear and logarithmic concentration scale.
- Individual concentrations (unadjusted and baseline-adjusted) will be provided overall for each subject on linear and logarithmic concentration scale (by-patient plot).
- Individual concentrations (unadjusted and baseline-adjusted) will be provided according to strata for each subject on linear and logarithmic concentration scale (by-patient plot).

For unadjusted concentrations, the mean overall baseline concentration will be presented as a dotted line in the overall graphic, and the respective average baseline of all subjects will be presented in the corresponding by-patient plots.

Descriptive statistics of calculated PK parameter for ALA and PpIX will be provided overall and according to strata.

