1. INTRODUCTION

The objective of this statistical analysis plan (SAP) is to specify calculation of pharmacokinetic parameters and the statistical analysis of the pharmacokinetic data in more detail than stated in the protocol for this Phase I clinical trial. The SAP does not change the analysis described in the protocol, but it should be precise enough to serve as a guideline for statistical programming and creation of tables for pharmacokinetics.

Safety and demographics evaluations will be described in another analysis plan provided by [REDACTED]

This SAP was developed with reference to the Protocol Version 2.0, 17-JAN-2020. Supplementary text gives a full specification of analyses and presentation. Deviations from the planned methods should also be summarized in Section 14. If additional analyses are required to supplement the planned analyses described in this SAP, they may be performed and will be identified in the CSR.

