7. PRESENTATION OF DATA

Tables, listings, and graphs will be produced in accordance with the principles outlined by the International Council of Harmonisation (ICH) E3 guideline.

Analysis of pharmacokinetics will be based on the pharmacokinetic analysis sets, if not stated otherwise.

If not stated otherwise, descriptive statistics for qualitative data include counts and percentages. The percentages will be calculated taking into account the number of subjects in the population under consideration. Descriptive statistics for quantitative data include: total number of subjects in the population under consideration, minimum, median, maximum, arithmetic mean, standard deviation, coefficient of variation (CV; if appropriate). For plasma concentrations and PK parameters related to concentrations, geometric mean, geometric standard deviation and geometric CV will also be presented.

Listings will be prepared including data that were not used for descriptive analysis for whatever reason. Data not used for descriptive analysis will be annotated accordingly.

In this Phase I PK study, missing observations will be assumed to be missing completely at random. Data will therefore be used to the largest possible extent without imputation of missing results.

In general, the scheduled measurement (rather than the control, if any) will be used in the statistical calculations for presentation in the tables of descriptive statistics (unless the scheduled measurement was considered unreliable, e.g. due to technical reasons, and needed to be replaced by an unscheduled repeat measurement). Although only one value per time point is selected for analysis, all data are presented in the data listings. Unscheduled readings will be annotated accordingly in the listings.

Data listings will include all subjects, i.e. evaluable and not evaluable. Subjects will be identified by the unique subject number.

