10. PHARMACOKINETIC PARAMETERS

The pharmacokinetic parameters for ALA and PpIX which will be derived from plasma using non-compartmental methods are listed in the table below. Values < LLOQ and negative values after baseline-adjustment will be set to zero for calculation of PK parameters. The mean of the three pre-dose samples (Visit 1, -0.5 h and 0 h predose at Visit 2) will be used for baseline adjustment.

Parameter	Description
C_{\max}	Observed maximum baseline-adjusted or unadjusted plasma concentration
AUC_{0-t}	Area under the baseline-adjusted as well as unadjusted plasma concentration-time curve from time zero to the last sampling time point at which the concentration was at or above lower limit of quantification (LLOQ); $t(\text{last})$ is defined as the last value > 0 after baseline adjustment. AUC_{0-t} will be calculated according to the linear trapezoidal formula
$AUC_{0-\infty}$	Area under the baseline-adjusted as well as unadjusted plasma concentration-time data extrapolated to infinity $(AUC_{0-\infty} = AUC_{0-t} + C_t/\lambda_z)$
$\%AUC_{t-\infty}$	Proportion of extrapolated part ($\%AUC_{t-\infty}$) $(1 - [AUC_{0-t}/AUC_{0-\infty}]) \cdot 100$
t_{\max}	time to reach C_{\max}
$t_{1/2,\lambda_z}$	apparent terminal half-life, calculated by $\ln 2/\lambda_z$
λ_z	Terminal rate constant, assuming first order elimination kinetics: $C(t) = \beta * \exp(-\lambda_z t)$. λ_z denotes the terminal rate constant estimated by linear regression analysis from a range of concentrations in the terminal phase estimated for each treatment and subject by log-linear regression from the linear portion of the logarithmic transformed concentration-time plot. The algorithm will start with the last 3 points with quantifiable concentrations and increases the number of involved points by 1 until the time point after C_{\max} restricted on time points after removing of the BF-200 ALA gel (all PK samples after the gel is wiped off [after 3h±10 min]). For each regression an adjusted R^2 will be computed: $\text{Adjusted } R^2 = 1 - \frac{(1 - R^2) \cdot (n - 1)}{n - 2},$ where n denotes the number of data points ($n \geq 3$). The regression with the largest adjusted $R^2 > 0.8$ will be selected for the estimation of λ_z using WinNonlin option "BestFit".

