10.1. Tabulation of Individual Data

Values $< LLOQ$ and negative values after baseline-adjustment will be set to zero and disregarded on logarithmic scale.

The results of unadjusted and baseline-adjusted plasma concentrations for ALA and PpIX measured will be listed for each subject with PK concentration data and tables will be prepared overall as well as by strata showing descriptive statistics for concentrations at each sampling time. Samples with an unquantifiable low concentration will be identified (i.e. $< LLOQ$).

Results of subjects excluded from the pharmacokinetic analysis sets will be listed together with the data of the other subjects and will be annotated accordingly. Subjects excluded from a pharmacokinetic analysis set will not be used for descriptive statistics of the respective analyte. Similar listings and tables (overall and by strata) will be prepared for pharmacokinetic parameters.

For each subject in the respective Pharmacokinetic Set, unadjusted and baseline-adjusted concentration-time curves will be plotted (showing each subject in one graph) overall as well as by strata on a linear as well as on a log-linear scale. Similar plots will be generated for the unadjusted and baseline-adjusted mean concentration-time curves (incl. figures showing the mean course without standard deviation on a linear as well as on a log-linear scale and a figure showing the mean course with standard deviation on a linear scale) overall as well as by strata.

For unadjusted concentrations, the mean overall baseline concentration will be presented as a line in the individual and geometric mean concentration graph

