14. CHANGES FROM THE PROTOCOL

Not applicable.

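### Negative baseline-adjusted concentrations are set to zero and zeros are left out of the geometric mean, so the adjusted geometric-mean table and curve are biased upward where the true rise is small

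*Protocol*

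**What the plan says.** The baseline-adjusted plasma concentrations of ALA and PpIX are the primary endpoints. Baseline is the arithmetic mean of three pre-dose samples: Visit 1, and -0.5 h and 0 h at Visit 2 (Protocol 10.2.6; PK SAP 10).

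The rules on low values are these:

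- Protocol 14.1: "Values < LLOQ and negative values after baseline adjustment are set to zero and disregarded when displaying data on a logarithmic scale".
- PK SAP 10.1, which governs the listings and the tables by sampling time: "negative values after baseline-adjustment will be set to zero and disregarded on logarithmic scale". PK SAP 10 has a similar sentence, but only for parameters: "negative values after baseline-adjustment will be set to zero for calculation of PK parameters".
- Protocol 14.3, on the geometric statistics of concentrations and parameters: "If a zero occurs in a sample, the corresponding geometric mean and geometric SD will be computed, omitting this value".

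The affected statistic and graphic are both planned:

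- Protocol 14.3: "Geometric mean concentrations (unadjusted and baseline-adjusted) will be given on linear and logarithmic concentration scale".
- PK SAP 7: "For plasma concentrations and PK parameters related to concentrations, geometric mean, geometric standard deviation and geometric CV will also be presented". PK SAP 10.1 also refers to a geometric mean concentration graph.

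The PK SAP states that "The SAP does not change the analysis described in the protocol", and its section "14. CHANGES FROM THE PROTOCOL" is marked not applicable. The protocol's rule on omitting zeros therefore stands. Neither document names one adjusted display as the main one.

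**The concern.** A subject whose post-dose value lies below his or her own baseline first becomes a zero and then disappears from the geometric mean and geometric SD. What remains is an average conditional on being above baseline. If nothing is absorbed, about half the subjects fall below baseline by chance, and the curve built from the other half still lies above zero. This happens even at 0 h, before dosing.

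The protocol's own evidence makes this situation plausible. Section 4.1 reports no PpIX elevation in the one-tube study and only a slight, transient ALA elevation. In a descriptive study the summary curves are the result. Here a primary-endpoint curve could show a rise produced by the handling rule, with successive points resting on different subjects.

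The adjusted arithmetic mean keeps the zeros but also uses floored values, so it is biased upward too, by less.

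**Working it through.** **Inputs.** The documents give no figure for this bias. Stratum size is 16, which follows from the protocol's own numbers: 12/(1 - 0.25) = 16. Baseline is the mean of three pre-dose values. Within-subject CV is not in the documents, so w = 10%, 20% and 30% are assumed. LLOQ is left out of the main calculation.

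**Closed form for no true rise, with normal error as an approximation.** The adjusted value is one post-dose value minus the mean of three others.

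- SD of the adjusted value = w × √(1 + 1/3) = 1.155w.
- Geometric mean of the positive half = SD × exp(-(0.5772 + 0.6931)/2) = 1.155w × 0.530 = 0.612w, which is 6.1/12.2/18.4% of baseline.
- Floored arithmetic mean = SD/√(2π) = 1.155w × 0.399 = 0.461w, which is 4.6/9.2/13.8%.
- At 0 h the sample is itself one third of the baseline, so SD = w × √(2/3) = 0.816w. The geometric mean is 0.816w × 0.530 = 0.433w, or 4.3/8.7/13.0%.

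**Simulation.** 25,000 strata of 16 per cell, lognormal within-subject error, and the same true rise for every subject. Results are in % of baseline, for CV 10/20/30%. The geometric mean is pooled over all positive values, and the medians are averages over strata.

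| True rise | Geometric mean, zeros omitted | Arithmetic mean, floored | Planned median |
|---|---|---|---|
| 0 | 6/12/18 | 5/9/14 | 1/2/3 |
| 10 | 10/16/22 | 11/15/20 | 10/9/9 |
| 20 | 17/21/26 | 20/23/27 | 20/18/17 |
| 50 | 47/42/43 | not needed | not needed |

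With no true rise:

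- 51/52/53% of values become zero. That leaves about 8 of 16 subjects (16 × 0.49 = 7.8; 16 × 0.47 = 7.5), with a 5th-95th percentile range of 5-11/4-11/4-11.
- Averaged over single strata of 16, the geometric mean is +7/+13/+20%.
- The signed mean is 0.
- At 0 h the pooled geometric mean is +4/+9/+13%.

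**Where the bias ends.** In this model the pooled geometric mean stops exceeding the true rise at about 11/22/33% of baseline. A second model used normal error and increments that differ between subjects (CV 60%, within the documents' 53-73%). Its ratio of planned to true geometric mean was 0.98/1.11/1.31 at an increment of 25% of baseline and 0.98/0.98/1.03 at 50%. The crossing point therefore depends on the model, but little or nothing is left by about 50%.

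**LLOQ.** Values below LLOQ are set to zero before dosing as well as after, so they lower the baseline. With LLOQ at 90% of the true level and CV 10%, the share of zeros falls from 51% to 43%, while the geometric mean goes from +6% to +17%.

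**Baseline drift.** At CV 10% and no rise, a Visit 1 sample 20% above or below the Visit 2 level (assumed) shifts the baseline by 20%/3 = 6.7%. The signed mean becomes -7% or +7%.

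**A one-third flag.** The share of strata of 16 with more than one third of values at or below zero is 91/92/93% at no rise, 10/54/73% at a 10% rise, 0/14/43% at 20% and 0/0/1% at 50%. A rule triggered by any such value would hit 0/51/90% of strata at a 50% rise.

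**The case against.** The strongest case against is that the plan already lets a careful reader see through the problem:

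- Protocol 5.3 makes unadjusted curves and parameters a tertiary objective, to cover cases where adjustment impairs the calculations. The unadjusted curves are drawn against a baseline line.
- Individual plots are planned, every adjusted value is listed, and PK SAP 7 has unused data annotated.
- The median and minimum are tabulated, and a minimum of zero shows that zeros occurred.
- Nothing is tested, and the error overstates systemic exposure; it does not hide it.

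Most of this stands. It limits the point to reporting, and it means the protocol's geometric-mean graphic need not be dropped or demoted. It does not remove the point. None of these items corrects the adjusted geometric-mean curve or gives its contributing n. Protocol 14.3 plans the number of observations, and PK SAP 7 counts the subjects in the population under consideration. Neither asks for the number of positive values, so a table could show 16 beside a geometric mean that rests on about 8.

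Readers might also infer more than the documents support:

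- That the adjusted geometric mean is inflated throughout the profile. It is not, once the rise is clear.
- That values below LLOQ simply add zeros. They can raise or lower the share of zeros.
- That the study would report PpIX absorption that did not occur. The median and the unadjusted curves would contradict such a reading, and no document makes the adjusted geometric mean the deciding display.

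**Conclusion.** The point holds for adjusted concentration summaries near baseline. The direction follows from the rules alone: flooring at zero and then omitting zeros conditions the geometric mean on a positive value.

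The size rests on the assumed within-subject CV of 10/20/30%. With no true rise the geometric mean is +6/+12/+18% of baseline pooled, or +7/+13/+20% averaged over strata of 16. The floored arithmetic mean is biased by less, the planned median is close to unbiased, and the signed mean is unbiased. Where samples lie near LLOQ the geometric-mean bias can be larger.

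No test, error rate or sample size is affected. It should still be fixed: the display concerns a primary endpoint, the near-baseline case is the one the earlier one-tube data suggest for PpIX, and the repair needs no new data.

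**What to change.** Amend PK SAP 7 and 10.1, for adjusted concentration summaries and mean curves only:

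1. At each nominal time, overall and by stratum, report the number of values above zero behind the geometric mean and the number at or below zero. Footnote the geometric-mean table and graphic as conditional on values above zero.
2. Add the arithmetic mean (SD) and median of the signed, un-floored change, with a curve on the linear scale. State one rule for values below LLOQ that applies equally to pre-dose and post-dose samples. Use this curve to judge whether there is a rise near baseline.
3. Do not interpret the adjusted geometric mean at time points where more than a pre-stated share of values, for example one third, is at or below zero.

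C_max, AUC_0-t and the unadjusted geometric-mean curves stay as planned, with a note that the adjusted parameters use floored values. Record the additions in PK SAP 14.

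The cost is some reprogramming, and small negative means that need a footnote and cannot be drawn on a log scale. Signed values remove the flooring bias but not a drift in baseline between Visit 1 and Visit 2.
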